10.6. Analysis of Pharmacokinetics

Serum TRC105 and plasma axitinib concentrations will be measured using validated methods and assessed for potential correlations with response, PFS, survival, adverse events, baseline characteristics and immunogenicity using descriptive statistics and models as appropriate.

10.7. Analysis of Protein Biomarkers

Angiogenic protein biomarker data for each patient who received at least one dose of TRC105 or axitinib study drug will be listed.

10.8. Analysis of Immunogenicity

Anti-Product Antibody (APA) concentrations will be measured using validated ELISA methods at the time points specified in the Schedule of Assessments. APA concentrations will be evaluated in the context of pharmacokinetic parameters and AE profiles.

10.9. Analysis of Archival Tumor Tissue

CD105 expression within the tumor vasculature will be quantified for each patient who received at least one dose of study drug and will be listed by cohort. Expression will be determined by IHC and/or by PCR. Other markers that may relate to efficacy or toxicity of TRC105 will also be explored.

11. DIRECT ACCESS TO SOURCE DATA/DOCUMENTS

All data entered on CRFs/eCRFs must be verifiable within the patients' source documents (written or electronic record). The Investigator/institution guarantees TRACON representatives and appropriate regulatory authorities direct access to the original source records for the duration of the agreed study record retention period. Printouts of source records that are electronically obtained and stored will not be acceptable for audit/inspection unless provided as certified exact copies and the data remains as meaningful and useful as in its original electronic state.

Legally protected subject identification and other personal health information must be securely stored with limited access by the participating institutions. Unless secure provisions are established by the institution to allow TRACON (or designee) to perform remote monitoring of electronic source records, TRACON (or designee) will review source records/data on site and will not remove any such protected health information.

12. QUALITY CONTROL AND QUALITY ASSURANCE

Monitoring visits to clinical investigator sites will be made by TRACON or its representatives periodically during the trial to ensure that GCPs and all aspects of the protocol are being followed.

The trial site will also be subject to possible inspection by the institutional review board (IRB) or independent ethics committee (IEC) or other appropriate regulatory authority. The trial site is also subject to quality assurance (QA) audits performed by TRACON or its representatives.

It is important that the Investigator(s) and their relevant personnel are available during the monitoring visits, audits, and inspections and that sufficient attention, time, and support is devoted to the process.

TRACON and its representatives will be governed by applicable regulations, good clinical practice standards, and internal SOPs for the conduct of monitoring visits and QA audits.

Protocol deviations will be captured in TRACONs electronic data capture system.

13. ETHICS

13.1. Health Authorities and Independent Ethics Committees/Institutional Review Boards

Before this study starts, the trial protocol, protocol amendments, informed consent forms, and any other information for patients will be submitted to the FDA, EMA or other national health authorities and to each IEC/IRB for review, as applicable. As required, the study will not start at a given investigational center before the IEC/IRB and health authority (where applicable) for the center gives written approval or a favorable opinion.

All correspondence and other evidence of appropriate and timely communications with the IRB/IEC should be retained in the Investigator/site files. Copies of all IRB/IEC approvals should also be forwarded to TRACON.

The only circumstance in which an amendment may be initiated prior to relevant approval is where the change is necessary to eliminate apparent immediate hazards to the patients. In that event, the Investigator must notify the IRB/IEC/health authorities and TRACON in writing within 5 business days after the implementation.

13.2. Ethical Conduct of the Study

The trial will be performed in accordance with the protocol, applicable local regulatory requirements and laws, and the International Conference on Harmonization Guideline on Good Clinical Practice, which supports the application of ethical principles that have their origin in the Declaration of Helsinki (see ICH E6, §2.1).

13.3. Written Informed Consent

The informed consent form language must be agreed upon by TRACON and the IRB/IEC and must be in compliance with ICH GCP, local regulatory requirements, and legal requirements. The informed consent information must not be changed without prior approval by TRACON and the IRB/IEC. The informed consent form used in this trial, and any changes made during the course of the trial, must be approved by both the IRB/IEC and TRACON, or designee, before use.

It is the responsibility of the Investigator to give each patient full and adequate verbal and written information regarding the objective and procedures of the trial and the possible risks involved. This information must be provided to the patient prior to undertaking any trial-related procedure. Patients must be informed about their right to withdraw from the trial at any time. Furthermore, it is the responsibility of the Investigator to ensure all subjects are appropriately informed before obtaining their signed and dated consent. Signatures from the investigator conducting the informed consent discussion should also be obtained prior to undertaking any trial-related procedure. Consent by a legally authorized representative is not permitted. Should an impartial witness be needed, ICHE6 requirements for impartial witnesses will apply.

The Investigator will retain the original of each patient's signed consent form in the Investigator/site files.

13.4. Patient Compensation

Patients will not be compensated for participation in this trial; this will be outlined in the patient informed consent form.

14. DATA HANDLING AND RECORDKEEPING

14.1. Inspection of Records

CRF's are required and should be completed for each patient who receives treatment with TRC105. Screen failure CRF's will not be collected. Nevertheless, records of potential patients identified and screened shall be retained on site screening logs. The completed original CRFs are the sole property of TRACON and should not be made available in any form to third parties without written permission from TRACON (except for authorized representatives of the HRA and in accordance with HIPAA regulations).

It is the Investigator's responsibility to ensure completion and to review and approve all CRF data. The investigator will sign off on his/her data per patient. These signatures serve to attest that the investigator has reviewed and approved the information contained on the case report forms and that the information is complete, accurate, and true. At all times, the Investigator has final personal responsibility for the accuracy and authenticity of all clinical and laboratory data entered on the CRFs.

The use of electronic CRFs (eCRFs) to capture study data using automated computerized data capture systems does not change the principles and requirements for collecting study data. The investigator still retains final personal responsibility for eCRF data and any associated data pertaining to it (e.g. metadata including any record of change to the originally recorded data). The investigator's signed approval of the eCRF data serves to attest that the electronic data and all of its associated metadata (including changes) has been reviewed and accepted as complete, accurate, and true for each patient in the study.

All CRF/eCRF data must be verifiable in the patient's source records by TRACON or its designee. TRACON will review CRF data as compared to source records in an attempt to identify missing and spurious data and notify the investigator of findings so that proper corrections can be made. TRACON representatives (monitors and auditors), and regulatory inspectors shall have direct access to the original source records in its original recorded format: electronic or hardcopy.

TRACON (or its designee) will perform all data management functions associated with the study. Data will be captured electronically. Automated data verification ("edit checks") will be used to ensure that the data are logical and consistent. Any inconsistencies will be queried for clarification or correction as appropriate by the clinical site.

14.2. Retention of Records

To allow for appropriate evaluations and/or audits by regulatory authorities or TRACON, the Investigator agrees to keep records, including the identity of all participating patients (sufficient information to link records, CRFs and hospital records), all original signed informed consent forms, copies of all CRFs, source documents, and detailed records of treatment disposition.

Essential documents will be retained until at least 2 years after the last approval of a marketing application in an ICH region and until there are no pending or contemplated marketing applications in an ICH region or at least 2 years have elapsed since the formal discontinuation of

clinical development of the investigational product. These documents should be retained for a longer period, however, if required by the applicable regulatory requirements or by an agreement with the sponsor.

If the Investigator relocates, retires, or for any reason withdraws from the study, then TRACON should be prospectively notified. The study records must be transferred to an acceptable designee, such as another Investigator, another institution. The Investigator must inform TRACON of any such transfer of responsibilities and properly identify the person or institution assuming the responsibility. The responsible investigator/institution must obtain TRACON's written permission before disposing of any records.

15. DEFINITION OF END TRIAL

15.1. End of Trial in all Participating Countries

End of trial in all participating countries is defined as the time at which all patients enrolled in the study have completed treatment on study.

For clinical investigational centers located in the EU, a declaration of the end of the clinical study will be made according to the procedures outlined in Directive 2001/20/ED, Article 10(c); for other countries, local regulations will be followed.

15.2. TRACON Discontinuation Criteria

Premature termination of this trial may occur because of a regulatory authority decision, change in opinion of the IRB/IEC, drug safety problems, or at the discretion of TRACON. In addition, TRACON retains the right to discontinue development of TRC105 at any time.

TRACON reserves the right to discontinue the trial prior to inclusion of the intended number of patients, but intends only to exercise this right for valid scientific or administrative reasons. If a trial is prematurely terminated or discontinued, TRACON will promptly notify the Investigator. After notification, the Investigator must contact all participating patients within a 28 day time period. As directed by TRACON, all trial materials must be collected and all CRF data must be completed to the greatest extent possible.

16. PUBLICATION OF TRIAL RESULTS

Publication of trial results is discussed in the Clinical Trial Agreement.

The sponsor is responsible for ensuring that the public has access to the appropriate information about the study by conforming to local and regional requirements for registration and posting of results.

The study will be listed in public databases on clinical studies www.clinicaltrials.gov and the European clinical trials database (EudraCT). The summary of the study results will also be available on www.clinicaltrials.gov and www.clinicaltrialsregister.eu websites.

17. FINANCING AND INSURANCE

Financing and Insurance are discussed in detail in the Clinical Trial Agreement.

20. APPENDICES

20.1. Appendix 1: National Cancer Institute (NCI) Common Terminology Criteria for Adverse Events (CTCAE)

The NCI CTCAE (Version 4.0) should be used to assess Adverse Events and may be reviewed on-line at the following NCI website:

http://evs.nci.nih.gov/ftp1/CTCAE/CTCAE_4.03_2010-06-14_QuickReference_5x7.pdf

20.2. Appendix 2: ECOG Performance Status

Grade	Performance
0	Fully active, able to carry on all pre-disease performance without restriction.
1	Restricted in physically strenuous activity but ambulatory and able to carry out work of a light or sedentary nature, e.g., light house work, office work.
2	Ambulatory and capable of all self-care but unable to carry out any work activities. Up and about more than 50% of waking hours.
3	Capable of only limited self-care, confined to bed or chair more than 50% of waking hours.
4	Completely disabled. Cannot carry on any self-care. Totally confined to bed or chair.
5	Dead.

20.3. Appendix 3: Axitinib Prescribing Information

<http://labeling.pfizer.com/ShowLabeling.aspx?id=759>

CTCAE	Common Terminology Criteria Adverse Events
DLT	Dose Limiting Toxicity
ECG	Electrocardiogram
ECOG	Eastern Cooperative Oncology Group
EGFR	Epidermal Growth Factor Receptor
g	Gram
HR	Hazard Ratio
ID	Identification
IRB	Institutional Review Board
kg	Kilogram
LOQ	Limit of Quantification
mg	Milligram
mL	Milliliter
mm	Millimeter
MTD	Maximum Tolerated Dose
NCI	National Cancer Institute
OS	Overall Survival
PD	Progressive Disease
PDGF	Platelet Derived Growth Factor
PFS	Progression Free Survival
PIGF	Placental Growth Factor
PR	Partial Response
PSA	Prostate Specific Antigen
PT	Preferred Term
RECIST	Response Evaluation Criteria in Solid Tumors
SAE	Serious Adverse Event
sCD105	Soluble CD105/endoglin
SD	Stable Disease
SOC	System Organ Class
sVEGFR2	Soluble VEGF Receptor 2
t _½	Half-Life
TGF-β	Transforming Growth Factor

Abbreviation or specialist term	Explanation
T _{max}	Time to Maximum Plasma Concentration
ULN	Upper Limit of Normal
VEGF	Vascular Endothelial Growth Factor

2. Objectives

2.1. Phase 1b

2.1.1. Primary Objective

To evaluate safety and tolerability and determine a recommended phase 2 dose for TRC105 when added to standard dose axitinib in patients with advanced renal cell carcinoma

2.1.2. Secondary Objective(s)

The secondary objectives are to evaluate pharmacokinetics (PK), immunogenicity and activity of the monoclonal antibody TRC105. The specific objectives of the efficacy analysis are:

- To look for preliminary evidence of antitumor activity when TRC105 is added to axitinib, by assessing response rate and progression-free survival
- To characterize the pharmacokinetic profile of TRC105 when given with axitinib
- To evaluate TRC105 immunogenicity by measuring anti-product antibody (APA) formation
- To explore the pharmacodynamic changes in circulating angiogenic biomarkers following treatment with TRC105 and axitinib

2.2. Phase 2

2.2.1. Primary Objective:

- To estimate the progression-free survival (PFS) of patients with advanced or metastatic RCC by RECIST 1.1 in patients treated with axitinib and TRC105 compared to those treated with axitinib alone, following failure of one prior VEGF inhibitor.

2.2.2. Secondary Objective(s):

- To estimate response rate by RECIST 1.1 and Choi criteria, including duration of response by RECIST 1.1 and Choi criteria
- To estimate the disease control rate (CR + PR + SD) at 16 weeks by RECIST1.1 and Choi criteria
- To determine the frequency and severity of adverse events as assessed by NCI CTCAE (Version 4.0)
- To evaluate TRC105 immunogenicity as measured by Anti-Product Antibody (APA) concentrations
- To explore the effects of TRC105 on circulating angiogenic protein biomarkers
- To characterize the pharmacokinetic profile of TRC105 and axitinib

3. Study Design

3.1. Phase 1

This is a multicenter, open-label, nonrandomized, phase 1b, dose-finding study of TRC105 in combination with standard dose axitinib in patients with advanced renal cell carcinoma. Escalating doses of i.v. TRC105 will be administered weekly beginning with Dose Level 1 in combination with oral axitinib given twice daily of each 28 day cycle. Additional intermediate doses (below the MTD established during the trial) may be explored based upon clinical, PK, and/or biomarker data.

Cohort	Number of Evaluable Subjects	Axitinib mg p.o., BID days 1-28	TRC105 mg/kg IV
-1	3-6	5	6 ^a
1 (starting dose)	3-6	5	8 ^a
2	3-6	5	10 ^a
Expanded Cohort 1	9-12 (up to 15 total at the MTD)	5	10 ^a
3	3-6	5	
 • 10 mg/kg weekly during cycle 1^b • 15 mg/kg every two weeks beginning with cycle 2 day 1^b
4	3-6	5	
 • 10 mg/kg weekly during cycle 1^b • 20 mg/kg every two weeks beginning with cycle 2 day 1^b
Expanded Cohort 2	At least 6 patients will be treated at the MTD (either cohort 3 or cohort 4 dose level)	5	
 • 10 mg/kg weekly during cycle 1^b • Either 15 or 20 mg/kg every two weeks beginning cycle 2 day 1^b

^a In cohort -1, 1, 2 and expanded cohort 1 TRC105 will be given weekly.

^b In cohorts 3 and 4 and Expanded Cohort 2, axitinib dosing will begin on cycle 1 day 1 and twice daily thereafter, and TRC105 will be administered weekly during cycle 1. The first weekly TRC105 dose will be split into two doses whereby 3 mg/kg is administered on cycle 1 day 1 and the balance is administered on cycle 1 day 4. Starting on cycle 2 day 1 and beyond, TRC105 will be administered every two weeks on days 1 and 15.

For cohorts 1 and 2, the DLT evaluation period, for purposes of dose expansion, will be the first 28 days of dosing axitinib and TRC105 together (e.g., from cycle 1 day 1 through cycle 1 day 28). Cycles are 28 days in duration.

For cohorts 3 and 4, the DLT evaluation will be the first 28 days of dosing axitinib with TRC105 every 2 weeks (e.g., from cycle 2 day 1 through cycle 2 day 28). Cycles are 28 days in duration.

Three patients will be initially enrolled and treated at each dose level. If none of these 3 patients experiences a dose-limiting toxicity (DLT) during the 28-day evaluation period, dose escalation will proceed following review of safety data with appropriate site staff including the principal investigators at all sites.

Patients are eligible for additional treatment until progression.

Regular safety and toxicity assessments are performed. Toxicities will be graded according to the NCI Common Terminology Criteria for Adverse Events (CTCAE), Version 4.0.

Toxicity Category	Drug-Related Toxicity/Grade
Hematologic	Grade 4 neutropenia for ≥ 5 days
	Febrile neutropenia: grade 4 neutropenia with fever > 38.5 °C both sustained over a 24 hour period.
	Neutropenic infection: grade ≥ 3 neutropenia with grade ≥ 3 infection
	Anemia \geq grade 3
	Grade > 4 thrombocytopenia or grade ≥ 3 thrombocytopenia and grade ≥ 3 hemorrhage
Nonhematologic	Grade 3 or 4 nonhematologic toxicity with the following exceptions: 
 • Nausea, vomiting or diarrhea for < 48 hours^a • Asymptomatic electrolyte abnormalities that are corrected to grade 1 or better in < 48 hours^b

^aPatients with related grade 3 or 4 diarrhea, nausea or vomiting for ≥ 48 hours despite optimal medical therapy will require a one-level dose-reduction of TRC105.

^bPatients with related grade 3 or 4 electrolyte abnormalities that persist for ≥ 48 hours will require a one-level dose-reduction of TRC105.

Up to 15 patients with advanced renal cell carcinoma will be treated at the weekly dosing MTD (or top dose level if a MTD is not determined) to further characterize safety and tolerability. At

least 6 patients with advanced renal cell carcinoma will be treated at the every two week dosing MTD (or top dose level if a MTD is not determined).

Dose escalation will be according to the following dose escalation schema, based on the occurrence of DLT.

- If none of three patients in a cohort experiences a DLT after completing Cycle 1, dose escalation may be authorized by the medical monitor or designee.
- If one of three patients in a cohort experiences a DLT, three additional patients will be enrolled at the same dose level. If no additional DLT is reported, dose escalation may be authorized by the medical monitor or designee.
- If more than one of three or more than one of six patients at a dose level develop a DLT, the maximum tolerated dose (MTD) will be considered exceeded. Patient enrolment and treatment at that dose level will be stopped. There will be no further dose escalation and the previous lower dose will be designated as the MTD.
- Patients, who discontinue the study prior to completing the 28 day DLT evaluation period (Cycle 1), for reasons other than a DLT, will be replaced.

3.2. Phase 2

The study population for safety will include all patients receiving at least a portion of one dose of study drug (TRC105 or axitinib). The study population for efficacy will include all randomized patients (intention to treat). The primary endpoint is PFS and the primary analysis will compare the TRC105 and control groups using a one-sided, stratified (by the randomization stratification factor) log-rank test at the $\alpha=0.10$ level of significance. The primary analyses of efficacy endpoints dependent on disease assessments (PFS, ORR and DR) will be performed in the intent-to-treat (ITT) population based on results of the central review of disease response and progression. Supportive analyses will be performed based on investigator assessments of disease response and progression. Pre-planned assessments of the primary endpoint will additionally be done based on number of prior therapies (one, two or three) and other known prognostic factors.

An interim analysis for futility will be conducted by the DMC when 55 events have occurred. At the interim analysis, the conditional power based on the observed hazard ratio (HR) will be estimated. If the conditional power is less than 25%, the DMC may recommend to the sponsor that the study be terminated for futility. However, this interim analysis will not consider the possibility of early termination on the basis of superior efficacy.

4. Sample Size Determination

4.1. Phase 1

The number of patients to be evaluated in this study is based primarily on sound clinical considerations established in dose-finding designs in Oncologic studies. This 3+3 dose escalation trial is expected to enroll approximately 18 patients. The final sample size will depend on the number of DLTs observed at the different dose levels.

4.2. Phase 2

A hazard ratio (HR) of 0.67 is considered to be clinically relevant. Based on 1:1 randomization and the use of a one-sided log-rank test at the $\alpha=0.10$ level of significance, 115 events are required in order to have 80% power to detect a HR of 0.67. The expected PFS of patients treated with axitinib who have progressed following first line treatment with a VEGFR TKI is 4.8 months. Based on a planned accrual period of 12 months, and a minimum follow-up period of 4.3 months, approximately 150 patients will be required. Timing of the final analysis of PFS will be determined by the sponsor based on the expected total number of events that define PFS and the timing of these events, and may occur prior to the occurrence of 115 events.

5. Analysis Population

The safety population includes all patients who receive at least a portion of one dose of the study drug, TRC105 or axitinib (phase 2 portion).

The phase 2 study population for efficacy will include all randomized patients (intention to treat).

The Phase 1b study population for efficacy will include all patients who receive treatment with axitinib and TRC105.

6. General Analysis Comments

Summary statistics will include frequencies and percents of responses in each category for discrete measures; and may include means, medians, standard deviations, minimum and maximum values for continuous measures. Listings of data represented on the Case Report Form (CRF) will be provided.

SAS[®], Version 9.0 or higher or R version 2.15 or higher, will be used to perform all statistical analyses.

7. Missing Data

All data collected, including unscheduled visits, will be presented in the data listings. Summary tables will generally be limited to planned visits.

In all analyses, except for partial dates, it is expected that only observed values will be presented; no imputation of missing data will be conducted. Partial dates will be imputed according to the following table. CRFs that are not listed below are not expected to contain partial dates. CRF versions may change. Only if a change impacts the imputation of a partial date will the SAP be amended.

Planned Imputation Methods for Partial Dates

CRF	Field	Planned Imputation Method	
		Month and Year Given	Year Given
Adverse Events	Date of Onset	First of Month	Jan 01 of Year
	Date of Resolution	Last day of Month	Dec 31 of Year
Concomitant Medications	Start Date	First of Month	Jan 01 of Year
	Stop Date	Last day of Month	Dec 31 of Year
Concomitant Treatment	Start Date	First of Month	Jan 01 of Year
	Stop Date	Last day of Month	Dec 31 of Year
Informed Consent Reconsent	Date of Consent/Reconsent	Last day of Month	Dec 31 of Year
Medical History and Baseline Emergent AE	Start Date	First of Month	Jan 01 of Year
	Stop Date	Last day of Month	Dec 31 of Year
Primary Diagnosis	Date of Diagnosis	Last day of Month	Dec 31 of Year
Prior Cancer Surgery	Date of Surgery	Last day of Month	Dec 31 of Year
Prior Cancer Therapy	Start Date	First of Month	Jan 01 of Year
	Stop Date	Last day of Month	Dec 31 of Year
	Date of Progression on Therapy	Last day of Month	Dec 31 of Year
Prior Radiation Therapy	Start Date	First of Month	Jan 01 of Year
	Stop Date	Last day of Month	Dec 31 of Year
Demography	Birth Date	15 th of the Month	Jun 15 of Year

8. Patient Accountability and Patient Disposition

The number enrolled, the number of doses received and the number of cycles completed (per Section 12.1) will be presented for each dose level for the phase 1 portion and by treatment group for the phase 2 portion. A summary of reasons for withdrawal will be provided. The number of patients in the safety populations will also be presented. Patient disposition, including reasons for discontinuation, and number of cycles completed will be listed.

9. Demographics and Baseline Characteristics

Demographics and baseline characteristics will be summarized by dose level. Demographic variables, including age, gender, and race will be summarized in a tabular form.

Initial diagnosis, prior cancer surgery, prior radiotherapy, prior cancer therapy, and medical history will be listed. Initial diagnosis, prior cancer surgery, prior radiotherapy, and prior cancer therapy will also be summarized by dose level for the phase 1 portion and by treatment group for the phase 2 portion.

10. Concomitant Medications and Treatments

A listing of all concomitant medications and treatment will be provided by patient, drug name, start and stop dates, whether the medication or treatment was ongoing. Concomitant medications will be coded by using WHO Drug Dictionary version September 2012.

11. Efficacy Endpoints

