4.1.1.1. Phase 1b Overview

This is a multicenter, open-label, nonrandomized, phase 1b, dose-finding study of TRC105 in combination with standard dose axitinib in patients with advanced RCC. Escalating doses of i.v. TRC105 will be administered weekly beginning with Dose Level 1 in combination with oral axitinib given as 5 mg p.o. BID daily. Intermediate dose TRC105 (below the MTD established during the trial) may be explored based upon clinical, PK, and/or biomarker data.

Weekly Dosing:

Dosing will begin at 8 mg/kg (cohort 1) however a -1 cohort has also been included (6 mg/kg) and will be enrolled if 8 mg/kg TRC105 plus axitinib exceeds the MTD. The first weekly TRC105 dose will be split into two doses whereby 3 mg/kg is administered on cycle 1 day 1 and the balance is administered on cycle 1 day 4. The entire weekly dose of TRC105 (6, 8 or 10 mg/kg) is then given on cycle 1 day 8 and weekly thereafter in combination with oral axitinib given as 5 mg p.o. BID. Those who tolerate TRC105 without any infusion reactions may be eligible for reduced infusion durations and decreased premedication (see [Section 6.1.6](#)).

Every Two Week Dosing:

In cohort 3 (10 mg/kg weekly during cycle 1; 15 mg/kg every two weeks beginning with cycle 2 day 1) and cohort 4 (10 mg/kg weekly during cycle 1; 20 mg/kg every two weeks beginning with cycle 2 day 1) the first weekly TRC105 dose will also be split into two doses whereby 3 mg/kg is administered on cycle 1 day 1 and the balance is administered on cycle 1 day 4. Starting on cycle 2 day 1 and beyond, TRC105 will be administered every two weeks on days 1 and 15.

After 2 cycles of treatment, patients who demonstrate a response of complete response (CR), partial response (PR) or stable disease (SD) will be eligible for additional treatment until progression.

Patients who exit the study for reasons other than drug-related dose-limiting toxicity prior to completion of the first 28-day cycle will be replaced. Inpatient dose escalation of TRC105 is not allowed.

Table 5: Dose Levels

Cohort	Number of Evaluable Subjects	Axitinib mg p.o., BID days 1-28	TRC105 mg/kg IV
-1	3-6	5	6 ^a

Cohort	Number of Evaluable Subjects	Axitinib mg p.o., BID days 1-28	TRC105 mg/kg IV
1 (Starting Dose)	3-6	5	8 ^a
2	3-6	5	10 ^a
Expanded Cohort 1	9-12 (up to 15 total at the MTD)	5	10 ^a
3	3-6	5	
 • 10 mg/kg weekly during cycle 1^b • 15 mg/kg every two weeks beginning with cycle 2 day 1^b

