10.3. Definition of Analyzed Study Populations

The following study populations will be considered when reporting study results:

- For Phase 1b, the study population for safety includes all patients receiving at least a portion of 1 dose of TRC105.
- For Phase 1b, patients with treatment-related DLT and those without DLT who received less than the prescribed dose of TRC105 or axitinib due to documented toxicity in Cycle 1 will be considered evaluable for dose-escalation purposes. Only those patients who are deemed "ineligible" or who receive no therapy will be eliminated from the analysis. Ineligible patients who receive therapy will not be included in the assessment of efficacy endpoints, but their data will be included in the assessment of all adverse event reporting

-
- For Phase 1b, the study population for efficacy will include all safety population patients who have baseline and follow-up tumor measurements as required for assessment by RECIST 1.1.
 - For Phase 2 the study population for safety includes all patients receiving at least a portion of 1 dose of TRC105.
 - For Phase 2, the study population for efficacy will include all randomized patients (intention to treat).

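### SAP 3.1 gives two conflicting DLT windows for cohorts 3 and 4: Cycle 2 in the cohort-specific text, Cycle 1 in the escalation and replacement bullets

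*SAP*

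**What the plan says.** SAP 3.1 (Phase 1) describes cohorts 3 and 4 as receiving 10 mg/kg weekly in Cycle 1 and then switching schedule. For cohort 3 the switch is to "15 mg/kg every two weeks beginning with cycle 2 day 1"; for cohort 4 it is to 20 mg/kg from the same day. The section then sets the window by cohort: "For cohorts 3 and 4, the DLT evaluation will be the first 28 days of dosing axitinib with TRC105 every 2 weeks", glossed as cycle 2 day 1 to day 28. Its first escalation sentence refers to the 28-day evaluation period without naming a cycle.

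Later in the same section the SAP introduces a list of four bullets: "Dose escalation will be according to the following dose escalation schema, based on the occurrence of DLT". The first reads "If none of three patients in a cohort experiences a DLT after completing Cycle 1, dose escalation may be authorized". The fourth deals with patients who discontinue "prior to completing the 28 day DLT evaluation period (Cycle 1), for reasons other than a DLT, will be replaced". Neither is limited to the weekly cohorts. The second bullet (1 DLT in 3) and the third (MTD exceeded) name no cycle.

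The protocol also carries both versions. The synopsis and 4.1.1.1 give the Cycle 2 window for cohorts 3 and 4, replace patients by reference to the 28-day DLT period, and set evaluability in Cycle 1 for cohorts -1, 1 and 2 and in Cycle 2 for cohorts 3 and 4. But 4.1.1.1 also says that patients who exit for reasons other than drug-related DLT "prior to completion of the first 28-day cycle will be replaced". Section 10.3 says of all Phase 1b that patients with DLT, or given less than the prescribed dose "due to documented toxicity in Cycle 1 will be considered evaluable for dose-escalation purposes".

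**The concern.** Cycle 1 of cohorts 3 and 4 does not contain the dose that those cohorts exist to test. It is 10 mg/kg weekly with a split first dose, the regimen of cohort 2, which protocol 2.3.4 reports as already given to 15 patients. A decision taken at the end of Cycle 1 therefore carries no information about 15 or 20 mg/kg every two weeks.

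Three things depend on the window: whether cohort 4 may open, which early leavers are replaced, and who enters the DLT denominator. The last feeds the DLT summary and listing planned in SAP 12.2 and the every-two-week MTD call, which decides whether 15 or 20 mg/kg is used if Phase 2 moves to that schedule.

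Timing matters for this drug. Protocol 2.3.1.3 reports that three of four monotherapy patients at 15 mg/kg weekly developed grade 3 anemia in Cycle 2. That was a different and more intensive schedule, so it says nothing about the rate to expect here. It does show that an event on this trial's DLT list can first appear after Cycle 1.

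**Working it through.** **Step 1. The rules side by side, for cohorts 3 and 4.**

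| Decision | Cohort-specific text | Unrestricted text |
|---|---|---|
| DLT window | Cycle 2, days 1 to 28 (SAP 3.1; protocol synopsis and 4.1.1.1) | Cycle 1 (SAP 3.1, bullet 4) |
| Escalate after 0 of 3 | 28-day evaluation period (SAP 3.1; protocol synopsis and 4.1.1.1) | After Cycle 1 (SAP 3.1, bullet 1) |
| Replace an early leaver | Before the end of the 28-day DLT period (protocol synopsis and 4.1.1.1) | Before the end of Cycle 1 (SAP 3.1, bullet 4; protocol 4.1.1.1) |
| Evaluable if under-dosed for toxicity | In Cycle 2 (protocol synopsis and 4.1.1.1) | In Cycle 1 (protocol 10.3) |

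**Step 2. Exposure when the decision is taken.** The every-two-week dose starts on cycle 2 day 1. At the end of Cycle 1, the number of cohort 3 patients who have received it is zero.

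**Step 3. The plan's own figure.** Protocol Table 22 gives the probability of escalating under the 3+3 rule. With true DLT rate p, escalation needs 0 of 3, or 1 of 3 followed by 0 of 3:

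P(p) = (1−p)³ + 3p(1−p)² × (1−p)³

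- p = 10%: 0.729 + 0.243 × 0.729 = 0.906 (table 0.91)
- p = 30%: 0.343 + 0.441 × 0.343 = 0.494 (table 0.49)
- p = 50%: 0.125 + 0.375 × 0.125 = 0.172 (table 0.17)
- p = 70%: 0.027 + 0.189 × 0.027 = 0.032 (table 0.03)

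All ten entries reproduce.

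**Step 4. The same rule under each window.** Let p1 be the DLT rate in Cycle 1 (10 mg/kg weekly) and p2 the rate in the first 28 days of the every-two-week dose. The documents give neither, so both are assumptions. With the Cycle 2 window, the chance of escalating from cohort 3 is P(p2). If Cycle 1 is used at both stages it is P(p1), whatever p2 is.

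| p1 | P(p1) | minus P(30%) = 0.494 | minus P(50%) = 0.172 | minus P(70%) = 0.032 |
|---|---|---|---|---|
| 5% | 0.973 | 0.479 | 0.802 | 0.941 |
| 10% | 0.906 | 0.412 | 0.734 | 0.874 |
| 20% | 0.709 | 0.214 | 0.537 | 0.677 |

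The excess runs from 0.21 to 0.94 over this grid. If p2 is no higher than p1 there is none; for p1 = 20% and p2 = 10% the sign reverses (0.709 − 0.906 = −0.198, from unrounded values).

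Bullet 2 names no cycle, so a narrower reading applies Cycle 1 only to the 0-of-3 route in bullet 1. That route alone has probability (1−p1)³: 0.857, 0.729 and 0.512 for p1 = 5%, 10% and 20%. These are lower bounds, and over the same grid they exceed P(p2) by 0.512 − 0.494 = 0.02 up to 0.857 − 0.032 = 0.83.

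**Step 5. Replacement.** Take a cohort 3 patient who completes Cycle 1 and leaves early in Cycle 2 without DLT. Under the protocol's cohort-specific sentence the patient is replaced. Under SAP bullet 4 the patient has completed the DLT period and is not.

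**The case against.** The strongest reply is that the design is settled and only leftover wording remains. The Cycle 2 window appears in the SAP and twice in the protocol. The protocol defines a DLT as a listed toxicity within the 28-day evaluation period, so on that definition a cohort 3 patient cannot be declared DLT-free at the end of Cycle 1. Bullet 1 says only that escalation may be authorised, and the general escalation sentence requires a safety review with the principal investigators. This largely stands: premature escalation would need one general bullet to be followed over explicit cohort-specific text. It does not remove the contradiction, because the SAP introduces the bullets as the schema that escalation will follow, and bullet 4 redefines the DLT period itself as Cycle 1.

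A reader might infer more than the documents support:

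- That Cycle 1 is the DLT window for every cohort. The same SAP section says otherwise, and only two of the four bullets name Cycle 1.
- That up to six patients per cohort could be judged with no exposure to the test dose. The bullet that expands to six names no cycle.
- That Table 22 is wrong. It is right as printed, and describes cohort 3 when the Cycle 2 window is used.
- That protocol 10.3 makes a patient who leaves in Cycle 2 without DLT evaluable. It covers patients with DLT or reduced dosing for toxicity, so for cohorts 3 and 4 it is incomplete rather than permissive. The replacement sentence in 4.1.1.1 can also be read alongside the cohort-specific one.
- That an inadequately tested regimen could pass straight into Phase 2. At least 6 patients are to be treated at the every-two-week MTD, the recommended dose follows a review of toxicity and pharmacokinetics, and Phase 2 use waits for completion of cohorts 3 and 4 and for sponsor notification.

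**Conclusion.** The point holds as an internal contradiction in SAP 3.1, with matching unrestricted Cycle 1 wording in protocol 4.1.1.1 and 10.3. Followed literally, bullets 1 and 4 would let cohort 4 open with no exposure to the cohort 3 every-two-week dose and would leave a DLT-free Cycle 2 leaver unreplaced; Table 22 would then not describe that escalation step. The scope is narrow. Cohort 3 to cohort 4 is the only listed escalation affected, and for cohort 4, the top level, the wording bears only on replacement and the every-two-week MTD call. The probabilities in the working illustrate the possible size under assumed DLT rates; they do not predict what happened or will happen. That the contradiction exists depends on no assumption. The harm depends on the schema being applied over the cohort-specific text.

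**What to change.** Reconcile the cohort-specific window and bullets 1 and 4 in SAP 3.1, the Phase 1b methodology in the protocol synopsis, both replacement sentences and the evaluability sentence in protocol 4.1.1.1, and the Phase 1b evaluability bullet in protocol 10.3. Each should state the same DLT window for a given cohort, for escalation, replacement and evaluability alike; bullets 2 and 3 could refer to that window too. Which window applies is for the sponsor and investigators to confirm. The cost is a few words in each document, with no change to sample size, dose levels or Table 22.
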